**2. RESEARCH PLAN**

Purpose of Study:
This study will investigate if mindfulness training via a smartphone mobile app is effective in improving OA-related knee pain.
Hypotheses, Research Questions, or Objectives:

 
• Objective 1: Test whether use of a mindfulness mobile app improve knee pain in adults with knee OA among active duty and other DoD beneficiaries.
 
• Objective 2: Evaluate if self- reported, health-related quality of life and mindfulness scores predict response to mindfulness treatment in OA.
 
• Null Hypothesis 1: A mindfulness mobile app has no effect on knee pain in adults with knee OA.
 
• Alternative Hypothesis 1: A mindfulness mobile app improves knee pain in adults with knee OA.
 
• Null Hypothesis 2: Self- reported, health-related quality of life and mindfulness scores have no effect on response to mindfulness treatment in OA.
 
• Alternative Hypothesis 2: Self- reported, health-related quality of life and mindfulness scores predict response to mindfulness treatment in OA.
 

Significance:
Osteoarthritis (OA) is a major cause of disability in the United States and is expected to affect 26% of Americans by 2040  . Studies of the socioeconomic burden of OA demonstrate a 2-4 fold increase in healthcare expenditures for people with OA as compared to non-affected controls  . In addition, associated healthcare costs continue to rise: recent estimates of insurer and out of pocket healthcare costs of osteoarthritis exceed \$185 billion USD per year with another \$10 billion lost from absenteeism at work  .

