To date, mindfulness studies involving chronic pain conditions have involved manpower- intensive interventions (in-person mindfulness training, group therapy, multiple physician appointments, etc.), which are difficult to implement in busy clinical settings. Web- and mobile health applications (mHealth) may provide an effective alternative to these interventions. A 2016 systematic review of 10 web-based mindfulness training programs found that such facilitator- free interventions were effective in reducing depression and anxiety. To our knowledge, only one protocol to date has been published investigating the use of a mindfulness mobile app as an intervention for improving outcomes in chronic pain.

Our primary aim in this study is to determine if regular use of a mindfulness application improves pain outcomes in adults with knee osteoarthritis. Our secondary aim is to determine if self-reported Healthcare-Related Quality of Life (HRQoL) scores predict response to mindfulness treatment in OA. We hypothesize that the use of an mHealth intervention for mindfulness training may be an effective adjunct treatment of chronic knee osteoarthritis pain; specifically, that regular use of a mindfulness application will result in a statistically significant reduction in pain outcomes and improvement in physical function as determined by the KOOS scoring system. We also hypothesize that those with lower baseline self-reported HRQoL scores are more likely to see a greater improvement in their pain and function with use of a mindfulness application than those with higher baseline scores.

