## 6. DATA ANALYSIS

### Data Analysis:

### Outcome Measures:

To compare the effect of the mindfulness app intervention against the control: using an intention-to-treat paradigm, the two groups will be compared via one-way analysis of variance (ANOVA).

To compare the effect of a mindfulness app intervention among high and low strata of baseline pre-intervention SF-12 and FFMQ-15 scores: statistical calculation is based on the interaction effect in a 2-way analysis of variance (ANOVA) model with 5% two-sided significance level.

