### Sample Size Estimation/Power Analysis:

Based on the KOOS Minimal Detectable Changes in patients with knee OA of 10 with a Standard Deviation of 15, a sample size of 74 per group will have 80% power to detect such a difference based on Student's t test for independent samples with 5% two-sided significance level. Allowing for 25% dropout, the required sample size is 99 per group to accomplish the first aim.

However, to determine if high or low strata of baseline mindfulness affects pain outcomes, a sample size of 144 per group (72 in each SF12 stratum) will have 80% power to detect a difference of 10 points with a standard deviation of 15 points (i.e., no mindfulness effect in the high SF12 stratum vs. a 10-point mindfulness effect in the low SF12 stratum). Allowing for the aforementioned 25% dropout rate, we anticipate 180 participants per group or 360 total participants.

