### Statistical Analysis:

Using an intention-to-treat paradigm, the first primary aims will be statistically compared via one-way analysis of variance (ANOVA). The second primary aim will be statistically compared via two-way analysis of variance (ANOVA).

Missing primary outcome data will be acknowledged in the overall report of analysis. The primary outcome data is based on KOOS scoring system. Per the validated instructions of KOOS analysis, "as long as at least 50% of the subscale items are answered for each subscale, a mean score can be calculated. If more than 50% of the subscale items are omitted, the response is considered invalid and no subscale score should be calculated." In the event that the KOOS data is omitted, the participant will be regarded as a "drop out" and they will be included as such in the intent-to-treat analysis.

Subgroup analyses will be completed via 2-way ANOVA, stratified by FFMQ-15 and SF-12 scores. Subgroup analysis based on age, gender, comorbid behavioral health conditions, and duration of Knee OA symptoms may be considered.

Over-the-counter pharmacologic treatment of musculoskeletal pain is a common practice; given the near ubiquitous usage of these medications, this protocol does not preclude use of NSAIDs or acetaminophen. However, medication use will be monitored via weekly surveys and analyzed post-hoc as a potential confounder of the collected data.

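### Aim 2 sets the trial's size, but its interaction test is not pinned to one score, cut, time point or error rule, and it leaves out baseline KOOS pain at a cost in power

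*Combined protocol and SAP*

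**What the plan says.** **Test.** Section 6, Outcome Measures, states the aim: "To compare the effect of a mindfulness app intervention among high and low strata of baseline pre-intervention SF-12 and FFMQ-15 scores". It goes on: "statistical calculation is based on the interaction effect in a 2-way analysis of variance (ANOVA) model with 5% two-sided significance level". Section 6, Statistical Analysis, repeats both instruments: "Subgroup analyses will be completed via 2-way ANOVA, stratified by FFMQ-15 and SF-12 scores". No section gives a hierarchy, a split of the 5% or an adjustment, and no baseline KOOS term is named in the model.

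**Power basis.** Section 6, Sample Size Estimation/Power Analysis, opens with "to determine if high or low strata of baseline mindfulness affects pain outcomes, a sample size of 144 per group". It then places 72 participants per group in each SF12 stratum and describes the alternative as "no mindfulness effect in the high SF12 stratum vs. a 10-point mindfulness effect in the low SF12 stratum". Section 3g, Instrumentation, treats the SF-12 as a quality-of-life measure and the FFMQ-15 as the mindfulness measure.

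**Status and scope.** Section 2, Background, says: "Our secondary aim is to determine if self-reported Healthcare-Related Quality of Life (HRQoL) scores predict response to mindfulness treatment in OA". The alternative hypothesis in Section 2 is wider: "health-related quality of life and mindfulness scores predict response to mindfulness treatment in OA". Section 6, Statistical Analysis, says: "The second primary aim will be statistically compared via two-way analysis of variance (ANOVA". The same part of Section 6 also lists these tests as subgroup analyses (quoted above).

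**Outcome and data.** Section 3a defines the primary outcome as change in KOOS pain after the intervention, with surveys at 12, 26, 52 and 104 weeks. Visit 1 in Section 3 collects KOOS, SF-12 and FFMQ-15 at baseline.

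**The concern.** Aim 2 drives the size of the trial. The plan gives 99 per group (198 in all) for Aim 1 and 180 per group (360 in all) once the interaction is to be powered. The 198 is taken here as the plan's figure, without endorsing it as what Aim 1 needs.

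A test that carries this much enrolment should be fully identified in advance. As written, an analyst could stratify by the physical or the mental SF-12 score or by FFMQ-15, choose any cut, use any of four follow-up times, and still comply with the plan. A positive result on any one of these could be reported as confirming that a baseline score predicts response. The model also leaves unused a baseline measurement that every participant provides.

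**Working it through.** **Inputs from the documents.** Interaction contrast 10 points, SD 15, two-sided 5%, 72 per cell (144 per group), 25% dropout and 180 enrolled per group (Section 6, Power Analysis); 3 × 96 = 288 planned completers, or 144 per group (Section 6, Number of Subjects).

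**Assumptions.** The correlation between baseline and follow-up KOOS pain (ρ) and the correlation between SF-12 and FFMQ-15 (r) are not in the documents. ρ is taken as 0.3 to 0.7 and r as 0 to 0.7.

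**1. The plan's own figure.** With m per cell, the standard error of the difference of differences is SD × √(4/m).
- At m = 72: 15 × √(4/72) = 3.54. Noncentrality is 10/3.54 = 2.83 on 4 × 72 − 4 = 284 df, and power is **80.5%**. The stated 80% reproduces for one SF-12 interaction with equal strata.
- The plan's 25% dropout leaves 180 × 0.75 = 135 per group, or 67.5 per cell. The standard error is 15 × √(4/67.5) = 3.65 and power is **77.9%**. The two sections imply different completer counts, so both are carried forward.

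**2. Error across instruments.** This applies if either score may support the claim and neither truly modifies the effect.
- Two independent tests at 5%: 1 − 0.95² = 9.75%.
- Correlated scores split at the median: the two interaction statistics correlate at 2 × arcsin(r)/π, which is 0.49 at r = 0.7. The error is then 9.1%.
- Both SF-12 summary scores plus FFMQ-15, if independent: 1 − 0.95³ = 14.3%. This is an upper figure.

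**3. Baseline KOOS pain as a covariate.** If SD 15 is the SD of change, and baseline and follow-up SDs are equal, the residual SD is 15 × √((1 + ρ)/2).

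| ρ | Residual SD | Power, 144 per group | Power, 135 per group |
|---|---|---|---|
| no covariate | 15.00 | 80.5% | 77.9% |
| 0.3 | 12.09 | 93.8% | 92.3% |
| 0.5 | 12.99 | 90.2% | 88.3% |
| 0.7 | 13.83 | 86.4% | 84.1% |

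If 15 were instead the SD of the follow-up score, the residual SD would be 15 × √(1 − ρ²), or 14.31, 12.99 and 10.71. Power at 144 per group would be 84%, 90% and 98%. The change-score outcome in Section 3a makes the tabled reading the more natural one.

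**4. Splitting the 5% equally over both instruments.** At 0.025 each and 72 per cell, power falls to 71.7% unadjusted. It is 79-89% with the covariate (SD of change, ρ from 0.7 to 0.3).

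**The case against.** Four objections have weight.

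- **SF-12 is clearly the powered instrument.** This stands. A reader might infer from the mindfulness label that the text leaves open which instrument the 360 participants power. The documents do not support that. The power text names SF12 strata three times, and Section 2, Background, ties the aim to quality of life and predicts more benefit at lower scores. The label contradicts the calculation beside it and needs correcting. What remains open is the summary score, the cut and the time point. The 72 of 144 implies an equal split, but no rule is written.
- **The outcome is already a change score.** This stands. A reader might infer that an ANOVA without baseline KOOS is biased or invalid. It is not: baseline enters by subtraction and randomisation protects the comparison. The loss is precision only, and it applies to Aim 1 as well.
- **Subgroup or secondary analyses need no adjustment.** This stands in part. If the tests are reported separately as exploratory, leaving them unadjusted is defensible and the 9-10% does not apply. But Section 6 also calls the aim primary and sizes the trial on it, so the plan has to choose.
- **The power gain depends on a correlation the documents do not give.** True, which is why a range is shown. Every value in the range gives a gain.

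**Conclusion.** The point holds as a should-fix. The sample size arithmetic for a single SF-12 interaction is sound. What is missing is the specification that makes it a single test, together with a covariate that costs nothing.

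- **Firm from the text:** two instruments at one 5% level with no rule across them; a mindfulness label on an SF-12 calculation; no FFMQ-15 power calculation; no named SF-12 summary score, cut or KOOS time point; inconsistent status and scope for the aim.
- **Conditional:** error of about 9-10% (up to 14.3% over three independent tests) arises only if any one of the interactions may support a confirmatory claim. It should not be read as the error rate of the plan under every reading.
- **Dependent on assumptions:** the gain from 80.5% to 86-94% (144 completers per group) or from 77.9% to 84-92% (135) holds the contrast at 10 points with equal strata, and takes SD 15 as the SD of change with ρ between 0.3 and 0.7.

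**What to change.** 1. Add baseline KOOS pain as a covariate in the arm-by-stratum model.
2. Before outcomes are compared by arm, name one SF-12 summary score, split at the pooled baseline median of all randomised participants, at one named KOOS time point, as the single powered 5% interaction test. The documents do not settle physical or mental, so that choice is the investigators'. The median split matches the 72/72 assumption. Replace the mindfulness label in the power text with the chosen score.
3. Label the other SF-12 score and FFMQ-15 exploratory, or test them only if the powered test is significant, with a Holm adjustment. Naming one test avoids the power lost by splitting the 5%.
4. Give Aim 2 one status and one scope in the Section 2 hypotheses, the Section 2 background and Section 6. If it stays a primary aim, say how its 5% relates to that of Aim 1.

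**Cost.** Wording in Sections 2 and 6. No new data, visits or participants are needed, because all three questionnaires are already collected at Visit 1. The downside is that the scores not chosen face a stricter threshold or exploratory status.

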**a. Interventions and Observations:**

Participants will be re-surveyed at 12, 26, 52, and 104 weeks to evaluate long-term outcomes. The primary outcome measure will be post-intervention change in Knee injury and Osteoarthritis Outcome (KOOS) pain subscale. Secondary outcomes will include the other KOOS subscale scores, FFMQ outcomes, and SF-12 self-reported mental and physical health self-assessments at these same time intervals.

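### Aim 2, which sets the sample size, splits baseline SF-12 and FFMQ-15 into high and low strata without fixing the score or the cut; its 80% power assumes a 50/50 split, and a continuous moderator would be more efficient if moderation is roughly linear

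*Combined protocol and SAP*

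**What the plan says.** Section 6, Outcome Measures, compares the app effect across "high and low strata of baseline pre-intervention SF-12 and FFMQ-15 scores", using the "interaction effect in a 2-way analysis of variance (ANOVA) model with 5% two-sided significance level". Statistical Analysis calls this the second primary aim, repeats the two-way ANOVA, and adds subgroup analyses stratified by the same two instruments. Neither place says where high ends and low begins.

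Sample Size Estimation/Power Analysis opens the aim 2 calculation with the purpose "to determine if high or low strata of baseline mindfulness affects pain outcomes". The calculation itself is on the SF-12: "a sample size of 144 per group (72 in each SF12 stratum) will have 80% power", for an interaction of 10 points and an SD of 15. The assumed pattern is "no mindfulness effect in the high SF12 stratum vs. a 10-point mindfulness effect in the low SF12 stratum". After dropout this gives 180 per group, 360 in total, against 99 per group for aim 1.

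Section 3.a, Interventions and Observations, lists "SF-12 self-reported mental and physical health self-assessments" among the outcomes. Instrumentation likewise describes the SF-12 as covering physical and mental health. No section says which of the two defines a stratum.

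**The concern.** The factor on which the trial is sized is not defined. Three things are open: the instrument (mindfulness or SF-12), the SF-12 component (physical or mental), and the cut. A participant who is high on one SF-12 component and low on the other cannot be placed. Nothing in the text stops these choices from being made after outcomes are known, although nothing says that they will be.

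There are two further costs. The power statement relies on equal strata. No median rule is stated, and the Randomization text mentions no stratification by these scores, so nothing in the plan secures that equality. Also, reducing a numeric score to two levels usually discards information, in the one analysis that accounts for 162 of the 360 planned participants (360 − 2 × 99 = 162).

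**Working it through.** **Inputs.** From section 6: two-sided 5% level; SD 15; app effect 0 in the high stratum and 10 in the low stratum, so a 10-point interaction; 144 evaluable per group, 72 per cell. Assumptions not in the documents: the shape of the score distribution, and linear moderation. Both are used only in steps 3 and 4.

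**1. The plan's own figure.** For an interaction contrast over four equal cells, n per cell = 4 × [SD × (z₀.₉₇₅ + z₀.₈₀) / δ]² = 4 × [15 × 2.80 / 10]² = 70.6, so 71. With 72 per cell, SE = 15 × √(4/72) = 3.54 and 10/3.54 = 2.83. Normal-approximation power is Φ(2.83 − 1.96) = 80.7%; noncentral t gives 80.5%. The 144 per group reproduces.

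**2. Unequal strata, stratum effects held at 0 and 10.** With a fraction p in one stratum and N = 144 per group, SE = 15 × √[2/(Np) + 2/(N(1 − p))]. Information relative to an equal split is 4p(1 − p).

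| Split | Relative information | SE | Power (normal) | Power (noncentral t) |
|---|---|---|---|---|
| 50/50 | 1.00 | 3.54 | 80.7% | 80.5% |
| 55/45 | 0.99 | – | – | 80.1% |
| 60/40 | 0.96 | 3.61 | 79.1% | 78.9% |
| 65/35 | 0.91 | – | – | 76.7% |
| 70/30 | 0.84 | 3.86 | 73.6% | 73.4% |
| 80/20 | 0.64 | 4.42 | 61.9% | 61.6% |

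If moderation is instead linear in a normal score, the difference between stratum means grows a little as the cut moves off the median (10.38 points at 70/30, 10.97 at 80/20). The fall is then milder: 79.6% at 60/40, 76.4% at 70/30 and 69.6% at 80/20.

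**3. Information kept by a split.** For a normal score with linear moderation and a cut at c, the fraction kept is φ(c)²/[p(1 − p)]. At the median this is 2/π = 0.637, a loss of 36.3%. For linear moderation of other score shapes cut at the median, the computed losses are 25.0% (uniform), 34.8% (beta 5,2), 44.7% (gamma, shape 2) and 45.9% (t with 5 df). If the effect is a true step at the cut, the split loses nothing.

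**4. Power with the score left continuous.** Choose the slope so that median-split strata differ by the plan's 10 points: 10 / (2 × √(2/π)) = 6.27 points per SD. Then SE = 15 × √(2/144) = 1.77, 6.27/1.77 = 3.54, and Φ(3.54 − 1.96) = 94%; noncentral t gives 94.2%. A simulation of 4,000 trials at 144 per group gave 94% for the continuous score and 79% for the median split.

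**The case against.** The strongest reply is that the plan's only stated alternative is two-level, no effect in one stratum and 10 points in the other. If that were the truth and the cut fell at the step, the split would be efficient and a straight line would be the misspecified model. This stands as a limit on step 4: the documents give no evidence for linearity, and equally none for a threshold. The 0-versus-10 pattern is a sizing scenario, and a threshold would still have to be named.

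A second reply is that 72 per stratum implies a median split. That is a fair guess, but it is not written down, and it does not say which score is split.

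Four stronger readings are tempting and are not supported:

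- **That the stated power survives only with a median split.** Splits of 55/45 and 60/40 give 80.1% and 78.9%. A fixed cut might also fall near the median, since the documents give no score distribution.
- **That a third of the information is simply lost.** That figure depends on score shape and linearity.
- **That the SF-12 has no single score to cut.** The documents name none, but do not say that none exists.
- **That the plan contradicts its own graded hypothesis.** The Background says that "those with lower baseline self-reported HRQoL scores are more likely to see a greater improvement in their pain and function", but the sentence goes on to compare them with people who have higher scores. A two-stratum interaction can test that.

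**Conclusion.** The concern holds in a limited form. The moderator and its cut are undefined in the analysis that sets the sample size, and the power statement rests on equal strata that nothing secures. With the plan's effect pattern, the loss is under 2 points at 60/40, about 7 points at 70/30 (73%) and about 19 at 80/20 (62%).

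The efficiency gain from an uncut score, about 94% against about 80% power at 144 per group, is an illustration under a normal score and linear moderation, not a demonstrated loss. It is large enough to make the continuous model the better default, because it uses data already collected.

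The dropout allowance is a separate matter: 180 × 0.75 leaves 135 per group, where even a median split gives 77.9%. That shortfall should not be attributed to the choice of strata.

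**What to change.** - **Outcome Measures and Statistical Analysis:** replace the strata by a linear model of change in KOOS pain, at a named time point, on arm, continuous baseline score and arm × score. The interaction coefficient is the aim 2 test.
- **Name one powered moderator in advance.** This means reconciling baseline mindfulness with SF-12 in the sample size text and, if the SF-12 is chosen, stating physical or mental. Treat the remaining scores as secondary, so that several interaction tests do not all count as primary.
- **Sample Size Estimation/Power Analysis:** restate the power for this model, giving the assumed slope per SD and the residual SD.
- **Presentation:** report the app effect at, for example, the 25th and 75th percentiles of the score. If strata are kept for display, fix the cut at the pooled baseline median.

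The cost is revised text in three parts of section 6 and one new power calculation, with no added data collection or participants. The downside is the linear-interaction assumption, which a plot of change against baseline score by arm can check.

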### Sample Size Estimation/Power Analysis:

Based on the KOOS Minimal Detectable Changes in patients with knee OA of 10 with a Standard Deviation of 15, a sample size of 74 per group will have 80% power to detect such a difference based on Student's t test for independent samples with 5% two-sided significance level. Allowing for 25% dropout, the required sample size is 99 per group to accomplish the first aim.

However, to determine if high or low strata of baseline mindfulness affects pain outcomes, a sample size of 144 per group (72 in each SF12 stratum) will have 80% power to detect a difference of 10 points with a standard deviation of 15 points (i.e., no mindfulness effect in the high SF12 stratum vs. a 10-point mindfulness effect in the low SF12 stratum). Allowing for the aforementioned 25% dropout rate, we anticipate 180 participants per group or 360 total participants.

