#### **Screening Visit:**

- Obtain and document signed Informed Consent document and HIPAA Authorization.
- Review past medical history in Armed Forces Health Longitudinal Technology Application (AHLTA) to verify the inclusion/exclusion criteria including previous encounter, vital signs review, co-morbidities, demographics, problems list, confirmatory x-rays demonstrating radiographic evidence of knee osteoarthritis.
- We will ask the participants to complete the Screening Visit Medical history questionnaire.
- Record: Age at time of randomization, gender, Kellgren and Lawrence (KL) Grade score at time of enrollment, age at time of osteoarthritis diagnosis, prior knee osteoarthritis therapies to date, name of standard of care medications (over-the-counter and prescription), current email address (to be used for scheduling and weekly email reminders), height (in inches), weight (in pounds), history of prior injury to the affected knee(s), current level of exercise, physical therapy in the past year, and prior experience with mindfulness.

**Randomization:** Subjects will be randomized into 1 of 2 groups using block randomization with repeated measures:

- **Intervention Group:** Patient education regarding osteoarthritis, its natural history, and common treatments plus the mindfulness (intervention) app. They will be provided with a pre-paid 12-week subscription to the mindfulness application, and provided an in-person demonstration on how to use it, and the subscription license code will be recorded for the purposes of tracking use after the conclusion of the study. The intervention group will be asked to use the mindfulness app 10 minutes per day/5 days per week. To standardize Pack usage across all participants, users will be asked to complete the Headspace Essentials", "Pain Management", and "Physical Health" Session Packs.

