### Number of Subjects:

	# Planned to Enroll	# Enrolled	# Planned to Complete Study	TOTAL
Number of Subjects at Scott AFB	120	0	96	360
Number of Subjects at Travis AFB	120	0	96	
Number of Subjects at Nellis AFB	120	0	96	

*\*If any location recruits more subjects, they will be allowed to continue recruiting not to exceed the total number of subjects for all locations.*

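### The Aim 1 sample size of 74 per group (99 after dropout) does not follow from its printed inputs, which give 37 per group (50 after dropout)

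*Combined protocol and SAP*

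**What the plan says.** Section 6 of the combined protocol and SAP, under Sample Size Estimation/Power Analysis, gives the Aim 1 inputs in one sentence. The effect size is "Based on the KOOS Minimal Detectable Changes in patients with knee OA of 10 with a Standard Deviation of 15". The test is "based on Student's t test for independent samples with 5% two-sided significance level". The result is that "a sample size of 74 per group will have 80% power to detect such a difference". The next sentence inflates this: "Allowing for 25% dropout, the required sample size is 99 per group to accomplish the first aim".

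The following paragraph sizes Aim 2, the treatment-by-stratum interaction. It uses the same difference of 10 and SD of 15 and arrives at 144 per group (72 per SF-12 stratum) for 80% power. It then sets the enrolment: "we anticipate 180 participants per group or 360 total participants". The Number of Subjects table repeats the total of 360 and, in its column "Planned to Complete Study", lists 96 at each of three sites.

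**The concern.** A difference of 10 with an SD of 15 is a standardised effect of 0.67. A two-sided 5% t test with 80% power needs well under 50 per group for an effect that large, so 74 per group looks about twice too big. It is also exactly twice 37, the number the usual calculation gives.

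What is at stake is the sample-size statement for the primary outcome, change in KOOS pain. If 74 is wrong, then 99 after dropout is wrong too, and 80% is not the power at that size. If recruitment fell short of 360, 99 per group is the only Aim 1 number in the plan that a reader could use to judge whether the primary comparison was still adequately sized. The plan also never states what power Aim 1 has at the size it intends to enrol.

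**Working it through.** **Inputs, all from Sample Size Estimation/Power Analysis.** Difference δ = 10; SD σ = 15; two-sided α = 0.05; power 80%; independent-samples t test; dropout 25%. Equal allocation is not stated outright. It is implied by a single per-group figure and by the Screening Visit text: "Subjects will be randomized into 1 of 2 groups using block randomization".

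**Step 1: required size.** The normal approximation is

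n = 2(1.960 + 0.842)² σ²/δ² = 2 × 7.849 × 225/100 = 35.3, so 36 per group.

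The exact noncentral-t solution for the t test that the plan names is n = 36.31, so **37 per group, 74 in total**.

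**Step 2: power at candidate sizes.** Noncentrality = δ / (σ√(2/n)), with 2n − 2 degrees of freedom.

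| n per group | Standard error | Noncentrality | Power for 10 points |
|---|---|---|---|
| 36 | 3.54 | 2.83 | 79.7% |
| 37 | 3.49 | 2.87 | 80.8% |
| 74 | 2.47 | 4.06 | 98.1% |

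For 74 per group to have 80% power, the difference would have to be 6.95 points, or the SD about 21.6. Neither figure is printed.

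**Step 3: could another reading of the inputs give 74?** With δ = 10 and σ = 15 the per-group numbers are:

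- one-sided 5%: 28
- α = 0.025: 45
- 90% power: 49
- 95% power: 60
- inflation for a rank test: 39 to 43

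None gives 74.

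**Step 4: dropout.** The plan's own step reproduces from its own input: 74/(1 − 0.25) = 98.7, so 99. The division is right and the number fed into it is not. Corrected: 37/0.75 = 49.3, so **50 per group, 100 in total**.

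**Step 5: how the plan uses the SD in Aim 2.** For the interaction contrast across four cells, SE = σ√(4/n) with 4n − 4 degrees of freedom. At n = 72 per cell, SE = 15 × √(4/72) = 3.54 and power is 80.5%; at 71 it is 79.9%. The printed 72 per cell therefore reproduces with an SD of 15 used directly.

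**Step 6: Aim 1 at the planned enrolment.** The plan implies two completer counts: 180 × 0.75 = 135 per group from the 25% dropout, and 3 × 96 = 288, or 144 per group if split equally, from the Number of Subjects table.

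| Completers per group | Power for 10 points | Difference with 80% power |
|---|---|---|
| 135 | 99.98% | 5.1 points |
| 144 | 99.99% | 5.0 points |

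This high power comes from the Aim 2 sample size, not from the Aim 1 error.

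**The case against.** The strongest defence is that 15 may be the SD of a single KOOS score. The primary outcome is a change, and the sample-size text does not say which SD it means. If baseline and follow-up were uncorrelated, the change-score SD would be 15√2 = 21.2, and the t test would need 71.6, so 72 per group; 74 would then have 81.3% power. On that reading 37 per group would have only 51.6% power, and restating the requirement as 37 would go in the wrong direction.

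This does not rescue the figure. It gives 72 rather than 74, and it needs a zero correlation that the plan does not state. It also conflicts with the next paragraph of the same section: with an SD of 21.2 to 21.6, 72 per cell would give Aim 2 only about 50 to 51% power, not 80%. Either the Aim 1 number is wrong or Aim 2 is badly underpowered. What stands is that the sponsor should confirm which SD was used.

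A second defence is that the error does no harm. It overstates the need, Aim 2 sets the enrolment, and the plan gives 99 no formal role as a recruitment floor. All of that is true and limits the consequence. It does not make the statement reproducible.

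A separate matter should not be confused with this one. Aim 1 divides by 0.75 for dropout, whereas Aim 2 goes from 144 to 180 by multiplying by 1.25; division by 0.75 would give 192 per group. Likewise, 96 completers of 120 per site is a 20% loss, not 25%. The Aim 1 correction does not settle that.

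**Conclusion.** The concern holds. On the printed inputs the Aim 1 requirement is 37 per group, not 74, and 50 per group after 25% dropout, not 99. The power at 74 per group is 98.1%, not 80%. The discrepancy is a factor of two, far beyond rounding or a choice of formula.

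This rests on equal allocation and on taking the SD of 15 at face value, as Aim 2 does. That 74 is the two-group total (2 × 37) printed as a per-group number is the likely explanation, but the numerical finding does not depend on it.

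The practical effect is limited. Aim 1 is not underpowered, and correcting it leaves the planned 360 as it is. The statement for the primary aim should still be corrected, because neither its required size nor its power can be reproduced from the inputs beside it.

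**What to change.** In Sample Size Estimation/Power Analysis, restate Aim 1 as 37 per group (74 in total) for 80% power, and 50 per group (100 in total) after 25% dropout. Add one sentence giving the Aim 1 power at the planned enrolment: above 99.9% for a 10-point difference with 135 to 144 completers per group, and 80% for about 5 points.

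Before making the change, the sponsor should confirm that 15 is the SD intended for the outcome as analysed. If 74 per group came from a different SD, print that SD and recompute the Aim 2 power with it.

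If the SD of 15 is confirmed, the cost is a correction to two sentences and one added sentence. Enrolment, analysis and procedures do not change on account of this point.
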